7.7 Missed Injection Target Dose Timeline

Protocol Title: **CAB-RPV LA Implementation Strategies for High-Risk Populations**

In order to ensure that patients receive their injection within the 7 days of their target injection date, the following outline will be followed. This outline is applicable for any missed dose:

- **Day 1 Post Target:** The study team will outreach to the participant via their preferred communication method as specified in their locator form in order to encourage them to return within the following three days. The encounter will be tracked in the study Log Book.
- **Day 3 Post Target:** The study team will outreach again to the participant via the preferred communication method to encourage them to return the following day. The encounter will be tracked in the study Log Book.
- **Days 5-7 Post Target:** The study team will enlist BMC's ARCH and PT street-based outreach workers who are experienced with and successful at reaching and engaging high-risk patients. The outreach workers will conduct active outreach to the participant in the community to bring them in for a visit. If active outreach is unsuccessful, the study team will also use the contacts on the locator form to attempt to reach the participant. The encounter will be tracked in the study Log Book.
- **Upon Return Within 14 Days Post Target:** The study clinician will obtain a viral load and genotype. If the participant's viral load is less than 200 copies per mL, they will administer the CAB-RPV LA. If the participant's viral load is over 200 copies per mL, the study clinician will refer them to their primary care provider who will make the determination about whether or not an injection is appropriate. The encounter will be tracked in the study Log Book.
- **If participant returns after 15 days Post Target:**
 - **Missed Dose Occurs within 2 months of Initiation Injection:** The participant will be given a maintenance dose at their next contact with study staff (400mg/600mg 2 ml). The participant will then resume their normally scheduled injection plan, i.e. next injection scheduled to be given 25-32 days after maintenance dose administered.
 - **Missed Dose Occurs after first 2 months of injection:** The participant will be given a loading dose instead of their scheduled dosing amount (600mg/900 mg 3 ml). The participant will then resume their normally scheduled injection plan.

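### Section 7.7 sets the late-return dose by an undefined 2 months from initiation, not by days since the last injection, so a longer gap can draw the smaller dose

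*Combined protocol and SAP*

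**What the plan says.** Section 7.7 is an outline that is to be followed when an injection is missed, and its scope is wide: "This outline is applicable for any missed dose". It grades the response by how late the person is. The last two steps are headed "Upon Return Within 14 Days Post Target" and "If participant returns after 15 days Post Target".

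The second of these splits in two:

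- "Missed Dose Occurs within 2 months of Initiation Injection": a maintenance dose of 400 mg cabotegravir and 600 mg rilpivirine (2 ml), then the usual plan, with the "next injection scheduled to be given 25-32 days after maintenance dose administered".
- "Missed Dose Occurs after first 2 months of injection": a loading dose of 600 mg and 900 mg (3 ml), then the usual plan.

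Three other sections bear on who decides. Section 7.1 requires all activity to be on label. Section 7.4 requires injecting clinicians to have read the instructions for use. Section 7.11 gives the management of missed doses to the Infectious Disease providers on the study staff.

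**The concern.** The rule indexes the dose to time since treatment began. A participant's time without an injection is a different quantity, and the rule does not use it. Elsewhere the protocol does count from the last dose: Section 7.6 times the second injection from the first, Section 7.7 times the injection after a late maintenance dose from that dose, and Section 7.8 times the next injection from a dose given in error.

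The wording is also incomplete. The first branch names the start of its count, the initiation injection. Neither branch says whether the count ends at the missed target or at the return. The second branch does not say which injection it counts from, and 2 months is not given in days.

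The study is aimed at people at high risk of falling out of care, and Section 4.1 names resistance after non-adherence as a risk. Section 9.0 lists an incorrect loading dose, and 3 ml given in place of 2 ml, among the medication errors to report. Whether a 3 ml dose is correct or reportable should not depend on how a sentence is read.

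**Working it through.** The plan gives no figure to reproduce here; the check is a day count.

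**Inputs**

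- Interval between monthly injections: 25-32 days. Section 7.6 gives it for the second injection and Section 7.7 after a late maintenance dose. Assumption: it also holds for the third and fourth.
- Doses: initiation 600/900 mg, maintenance 400/600 mg (Section 7.0, medication regimen). A monthly participant's last dose before the third or the fourth injection is therefore 400/600 mg.
- 2 months: assumed to be 59-62 days (calendar months).
- Late return: 16 or more days past target, reading the step strictly.
- Initiation is day 0.

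**Step 1. Target dates.** Second: day 25-32. Third: 2 x 25 = 50 to 2 x 32 = 64. Fourth: 3 x 25 = 75 to 3 x 32 = 96.

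**Step 2. Branch when the count runs to the missed target.**

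| Missed injection | Target day | Against 59-62 | Late-return dose |
|---|---|---|---|
| Second | 25-32 | always within | 400/600 mg |
| Third | 50-64 | within if on or before the cut | 400/600 mg if within, otherwise 600/900 mg |
| Fourth | 75-96 | always after | 600/900 mg |

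For the second injection the dose never changes with lateness. At 60 days late (illustrative) the time since the initiation injection is 25 + 60 = 85 to 32 + 60 = 92 days, and the dose is still 400/600 mg.

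**Step 3. Gap against dose, third and fourth injections.** The gap is the interval plus the days late. The fourth at 16 days late has a gap of 25 + 16 = 41 to 32 + 16 = 48 days. The third at d days late has a gap of at least 25 + d. It exceeds every one of those fourth-injection gaps when 25 + d > 48, so d = 24, and the gap is then 25 + 24 = 49 to 32 + 24 = 56 days. For a third injection with its target on or before the cut:

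- third, 24 days late: 49-56 days since the last dose, 400/600 mg;
- fourth, 16 days late: 41-48 days since the last dose, 600/900 mg.

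The upper end is reachable under every cut: intervals of 27 and then 32 days put the third target on day 59. If the step is taken to start at day 15, the same sums give 23 days late (48-55 days) against 40-47 days.

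**Step 4. Branch when the count runs to the return.** Take a third injection due day 57 and given day 73, which is 73 - 57 = 16 days late. By target date, 57 is within 59-62, so 400/600 mg. By return date, 73 is beyond 62, so 600/900 mg. The earliest late return for any third injection is 50 + 16 = day 66, so on this reading all of them draw 600/900 mg and the inversion in Step 3 disappears. A missed second injection would also move to 600/900 mg once the delay exceeds the cut minus the target, a threshold between 59 - 32 = 27 and 62 - 25 = 37 days. If 2 months meant two 28-day cycles (56 days), the day-57 example would draw 600/900 mg on both readings, and the split would be confined to third targets on days 50-56.

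**Step 5. Bi-monthly schedule.** The switch is allowed after the second injection. Taking a bi-monthly interval as two of 25-32 days, the first bi-monthly target is day 75-96, past any cut, so the dose is always 600/900 mg. The gap at 16 days late is 50 + 16 = 66 to 64 + 16 = 80 days. A monthly participant in the same branch at the same lateness has 41-48 days.

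**Step 6. Day 15.** A return on exactly day 15 is neither within 14 days nor after 15 days.

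**The case against.** The strongest reply is that the text has one natural meaning. The outer step speaks of the return and the inner one of when the missed dose occurs, so the inner count should end at the target date. That is fair. The day-57 example then has one answer, 400/600 mg, and the return-date reading is possible but weaker. It is also true that the inversion and the two-dose example cannot both arise under one consistent reading. But the natural reading is the one that produces Steps 2 and 3, so it does not rescue the rule.

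A second reply is that a rule based on early versus later treatment is a legitimate form, and that nothing here proves a wrong dose. That stands. A reader might infer that 7.7 underdoses people who return late. The documents do not support this: they contain no missed-dose rule from the package insert and no pharmacological basis for choosing between the two doses.

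A third reply is that specialists manage missed doses, on label, having read the instructions for use (Sections 7.1, 7.4 and 7.11). This lowers the risk. It does not settle the point, because 7.7 states the milligrams itself, in an outline that is to be followed, and none of those sections says when to depart from it.

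Finally, bi-monthly participants are covered and their branch is not ambiguous. Step 5 shows only that one dose serves very different gaps.

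**Conclusion.** The concern holds in a limited form. Section 7.7 chooses the late-return dose without regard to days since the last injection. On its natural reading it gives 400/600 mg to a missed second injection at any lateness. Between monthly participants with the same last dose, it can give the smaller dose after the longer gap: 49-56 days against 41-48. The end of the count, the length of 2 months and day 15 are left open.

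This rests on 25-32 day intervals carrying through to the fourth injection and on 2 months meaning 59-62 days. The inversion needs the target-date reading and a third injection due on or before the cut; third injections due on day 63 or 64 always draw 600/900 mg.

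Two stronger readings should be resisted. One might count the share of possible third-injection dates on which the two readings disagree and take it as the share of participants affected. It would be a share of equally weighted dates, and the plan does not estimate how often anyone returns this late. One might also infer bias in the viral suppression comparison (H4). With 20 planned in Cohort 1 (Section 11.2), few such returns are likely, and nothing in the documents links them to that result. This is a dosing-safety instruction that should be corrected; it does not threaten the analysis.

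**What to change.** Rewrite the two late-return branches in days since the last injection received, with separate lines for the monthly and bi-monthly schedules. The study clinicians should set the cut-offs and doses from the package insert, which the on-label requirement and the training section already rely on. If a 2-month cut is kept anywhere, give it in days, use the same starting injection in both branches, and say whether it runs to the missed target or to the return. Make the last step begin at 15 or more days past target, so that day 15 has a branch.

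The cost is an amendment to a few bullets, submitted to the IRB as Section 13 provides, and a notice to the injecting clinicians. Injections are already recorded in the EHR (Section 10.1) and injection visits in the Log Book (Section 7.6), so no new visit, test, participant or data field is needed.

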7.6 Injection Process and Safety Procedures

For patients enrolled in Cohort 1, injection procedures will be as follows:

- 15 minutes prior to the scheduled appointment time, the study clinician will remove the injection from refrigeration.
- Injections will be administered by a licensed healthcare professional (physician, nurse, nurse practitioner).
 - a. A complete dose will include two injections: one injection of cabotegravir and one injection of rilpivirine.
 - b. Each injection will be administered at separate gluteal injection sites during the same visit, with the ventrogluteal site recommended.
 - c. The clinician will consider the body mass index (BMI) of the patient to ensure that the needle length is sufficient to reach the gluteus muscle. Longer needle lengths (not included in the dosing kit) may be required for patients with higher BMI (greater than 30 kg/m²) to ensure that injections are administered intramuscularly as opposed to subcutaneously.
- The clinician and the participant will determine the target date for the next injection, which will occur between 25-32 days from initial injection. This discussion will happen while the participant waits for 15 minutes to ensure that no immediate adverse effects occur. This encounter and next planned injection date will be documented in the study Log Book by study staff. During this 15-minute period, the participant may also complete follow-up questionnaires if they are due for their three-month or six-month follow-up survey.
- Once the participant receives their second injection, they may discuss with their clinician whether they want to continue to receive their injection monthly, or whether they want to move to a bi-monthly schedule. The same procedures (confirming appointments in advance, removal from refrigerator, injection administration, monitoring period post-injection, scheduling of next injection, documentation in study log) will be used for follow-up injections
- Once the participant has been enrolled for at least 6 months in the study, they will be given the option to remain on CAB-RPV LA
 - a. That administration can take place either at PT or at CID depending on the participants preferences
 - b. If the participant wishes to receive their injection at CID, the study clinician will reach out to the participants CID provider so that the participant can begin to schedule their injections at CID

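### Section 7.7 sets a viral load, genotype and 200 copies/mL referral rule for returns within 14 days of a missed injection, but none for later returns

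*Combined protocol and SAP*

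**What the plan says.** Section 7.7 (Missed Injection Target Dose Timeline) describes its own scope broadly: "This outline is applicable for any missed dose". It starts with outreach on days 1, 3 and 5 to 7 after the target date, then gives two branches for participants who come back.

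For a return within 14 days: "The study clinician will obtain a viral load and genotype". The injection is given if the viral load is below 200 copies/mL. Otherwise, "If the participant's viral load is over 200 copies per mL, the study clinician will refer them to their primary care provider", and that provider decides whether an injection is appropriate.

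The second branch opens with "If participant returns after 15 days Post Target" and splits by when the dose was missed. For a miss within 2 months of the initiation injection: "The participant will be given a maintenance dose at their next contact with study staff (400mg/600mg 2 ml". For a later miss: "The participant will be given a loading dose instead of their scheduled dosing amount (600mg/900 mg 3 ml". In both cases the participant then resumes the usual injection schedule.

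Section 4.1 (Potential Risks) lists resistance to cabotegravir and rilpivirine as a possible result of not keeping to the injections.

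On a separate point, the step in section 7.1 for participants who skip the oral lead-in describes viral suppression with a greater-than sign before 50 copies/mL. Section 5.1 and the screening text in section 7.1 both put suppression below 50.

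**The concern.** For any given target date, a participant who comes back later has gone longer without an injection. The plan writes down a virological check for the shorter delay and none for the longer one, and gives no reason for the difference. The late branch is also worded as an instruction to dose. Staff who follow it literally would re-dose after the longer gaps without first checking for viral rebound or resistance.

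What is at stake is participant safety and consistent conduct in Cohort 1. Late returns are foreseeable: section 1.2 names homeless individuals, active substance users and people who have fallen out of HIV care among the target groups, and section 4.1 calls dropping out of care the primary risk. No effect on the planned cohort comparisons is claimed.

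**Working it through.** The plan states no figure on this point, so there is none to reproduce. The check is a comparison of text, with one short calculation to show where the written safeguard stops.

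**Step 1. The branches of section 7.7 side by side**

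| Return after target date | Test stated | Threshold | Referral | Dose |
|---|---|---|---|---|
| Within 14 days | Viral load and genotype | 200 copies/mL | Yes, if over 200 | Given if below 200 |
| After 15 days, miss within 2 months of initiation | None | None | None | 400/600 mg |
| After 15 days, later miss | None | None | None | 600/900 mg |

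Read literally, day 15 itself and a viral load of exactly 200 are not assigned. Both are trivial wording gaps: a day-15 return is plainly not within 14 days, so only the late branch can apply.

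**Step 2. Does another section fill the gap?**

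- Section 7.1 says activities are on label, and section 7.4 says clinicians have read the product information. Neither states a test.
- Section 7.5 keeps an unused dose refrigerated until the participant is ready for it, with no mention of a test.
- Section 7.10 orders a viral load, but only after suspected accidental intravenous administration. It shows that the plan writes down an event-triggered viral load when it wants one.
- Section 7.11 gives the management of missed doses to the infectious disease providers on the study staff. It assigns responsibility and sets no rule.
- Section 9.0 has the study clinician advise on exclusion, referral and withdrawal. Again, no test is set.
- Sections 7.3 and 10.1 schedule record reviews at the data collection points and at 3 and 6 months. A missed dose does not trigger them.

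No section sets a test at a late return.

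**Step 3. Where the written test stops**

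Days since last injection = target interval + days late.

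Monthly interval: 25 to 32 days. Section 7.6 gives this for the second injection ("which will occur between 25-32 days from initial injection") and section 7.7 gives it after a late maintenance dose ("next injection scheduled to be given 25-32 days after maintenance dose administered"). Using it for every monthly interval is an assumption.

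- 14 days late: 25 + 14 = 39 to 32 + 14 = 46 days. Test stated.
- 16 days late: 25 + 16 = 41 to 32 + 16 = 48 days. No test stated.

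Bi-monthly interval: the documents give no day count, so two consecutive calendar months are assumed, 59 to 62 days.

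- 14 days late: 59 + 14 = 73 to 62 + 14 = 76 days. Test stated.
- 16 days late: 59 + 16 = 75 to 62 + 16 = 78 days. No test stated.

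The ranges overlap because the target interval varies. For one fixed target date, the longer delay always has the weaker written check.

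**The case against.** The strongest reply is that responsibility is already assigned. Section 7.11 places missed doses with infectious disease providers, who are the people who would order a viral load. The drug is approved, activities are on label, and the late branch can be read as a dose adjustment added to ordinary clinical assessment. For misses after the first 2 months it also adds something that the early branch lacks, a loading dose. Much of this stands: the text does not forbid testing, and testing may well happen. It does not explain the asymmetry, because the same providers manage returns within 14 days and the plan still wrote an explicit rule for them.

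A reader might infer more than the documents support:

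- *That late returners will be re-dosed untested, or harmed.* The text is silent on testing, and clinicians keep their judgment. The package insert is not available here, so a departure from the label cannot be shown either.
- *That someone who returns in time could slip into the late branch while waiting for a result.* Both branch headings classify by the day of return, so a participant back on day 12 stays in the early branch however long the laboratory takes. What remains is only that no waiting time is stated.
- *That the reversed sign in section 7.1 would let unsuppressed people start injections.* The same sentence calls these people suppressed, and screening already requires a value below 50.

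**Conclusion.** The concern holds as a gap in a written safeguard. Section 7.7 directs a dose after the longer delays without the viral load, genotype and referral rule that it requires after the shorter ones, and nothing elsewhere supplies them. Confidence is high on the text; clinical harm is not shown.

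The number affected cannot be estimated, because the documents give no late-return rate. It is some subset of the 20 participants planned for Cohort 1 (section 11.2), within a participation period of about six months. The outreach on days 1 to 7 should reduce it but does not cover those who still return late.

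The conclusion rests on reading the late branch as the instruction staff will follow, and on no test being set in material outside these documents. It should be fixed because the plan already contains the test and the threshold. The sign in section 7.1 is a minor correction with little expected effect.

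**What to change.** In section 7.7:

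1. Redefine the late branch as any return on day 15 or later, so that it adjoins the 14-day branch.
2. Require a viral load and genotype in that branch, with the same referral rule, written in both branches as below 200 versus 200 copies/mL or more. If the study clinicians consider the test unnecessary there, state the clinical reason.
3. Keep the existing maintenance and loading dose adjustments.
4. Have the study clinicians state whether the dose is given the same day, with the result acted on afterwards, or held until the result is known.

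In section 7.1, in the step for participants who skip the oral lead-in, change the sign to less than 50 copies/mL, to match section 5.1 and the screening text.

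The cost is a wording amendment and one blood draw per late return. Holding the dose adds a short delay to a gap that is already long; same-day dosing means that some doses are given before a result of 200 or more is known. That choice is clinical, and the plan should record it.

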7.8 Dosing Errors & Other Errors

All efforts will be made to ensure there are no dosing errors. However, the following procedures are in place to address dosing errors or other errors:

- **Dosing Error – Too Large of a Dose Administered:** The study staff will contact the participant immediately following recognition of error and inform them about their error. If dose was the equivalent or higher of the loading dose (600 mg/900 mg 3 ml), then study staff would change next target injection date to be 2 months after dose given in error, and then resume maintenance doses moving forward.
- **Dosing Error – Too Small of a Dose Administered:** Study staff will contact the participant immediately following the recognition of the dosing error.
- **Incorrect storage of Cabenuva:** If it is determined that the injection has been incorrectly stored, the affected doses will be disposed of in a hazardous waste container.
- **Healthcare Provider Needlestick Injuries:**
 - Wash/rinse wound or exposed area immediately.
 - Report incident to Study Staff Supervisor

Protocol Title: **CAB-RPV LA Implementation Strategies for High-Risk Populations**

- Exposed individual should call the BMC Working Well Clinic at [contact] or visit the clinic on the 7th floor of the Doctor's Office Building.
- Print and Complete all forms listed below that are found on the BMC Employee Hub:
 - Blood and Bodily Fluids Exposure Incident Form and scan and email to [contact]
 - Source Patient Requisition Form
 - Source Patient Testing Release Form – other staff member must consent patient, have both printed name and signature at the bottom of the page of source patient and ordering provider who consented patient
 - Test results are reported to the Working Well Clinic who will notify individual of results

